3.6 Statistical Methods

The results will be provided by treatment group and total (combined treatment group). There is no plan to do between treatment group comparisons.

3.6.1 Statistical Methods for Efficacy Analyses

The analysis of efficacy endpoints will be based on the FAS population. Unless specified otherwise, analyses will include all follow-up efficacy data collected for those participants who discontinued treatment.

The continuous endpoints will be analyzed using the longitudinal analysis of covariance (ANCOVA) model. In this model, response variable will be change from baseline. The model will include terms for treatment, visit, and the interaction of treatment by visit and baseline value as a covariate. Visit is treated as a categorical variable so that no restriction is imposed on the trajectory of the means over time. An unstructured covariance matrix will be used to model correlations among repeated measures. If the unstructured covariance structure fails to converge with the default algorithm, then the AR(1) structure can be used to provide initial values of the covariance parameters. This model uses the maximum likelihood principle to estimate the parameters and account for missing data in an implicit fashion. The change from baseline to each visit and 95% CIs will be estimated from this model. Baseline variable is defined as the last non-missing value prior to the treatment.

Categorical endpoints will be analyzed by calculating the percentage of participants in each response category at each timepoint. For some endpoints (change from baseline in LCQ total score, change from baseline in mean weekly CSD total score), percentage of participants meeting certain threshold values will also be provided. Only observed data will be included in the analysis.

Considerations for the analysis specific to the respective endpoints are provided below.

LCQ total score

Change from baseline in the LCQ total score will be analyzed using the longitudinal ANCOVA model above to estimate within-treatment change from baseline and corresponding 95% CI at each time point. Percentage of participants who had an increase in the total score of ≥ 1.3 points from baseline at each time point will also be summarized.

The Physical domain score will be considered as missing if there are 2 or more items are missing. If there is only 1 item is missing, the Physical domain score will be based on the actual non-missing items. Psychological domain score will be derived in a similar fashion. The Social domain score will be considered as missing if any item is missing. The LCQ total score will be considered as missing if any of the 3 domain scores is missing.

Mean weekly CSD total score

Change from baseline in the mean weekly CSD total score will be analyzed using the longitudinal ANCOVA model above to estimate within-treatment change from baseline and corresponding 95% CI at each time point. Percentage of participants who had a reduction in the total score of ≥ 1.3 and ≥ 2.7 points from baseline at each time point, respectively, will also be summarized.

The mean weekly total score will be considered missing if there are less than 4 non-missing days during the week prior to each visit. If there are less than 7 but at least 4 non-missing days during the week prior to a visit, the mean weekly total score will be based on the actual non-missing days of the week prior to the visit. Mean weekly subscales will be derived in a similar fashion.

EQ5D-5L

Change from baseline in the EQ5D-5L index utility score will be analyzed using the longitudinal ANCOVA model above to estimate within-treatment change from baseline and corresponding 95% CI at each time point. If a participant has a missing response to any of the five individual questions at a particular timepoint, then the entire response for that participant at that timepoint will be considered missing.

EQ VAS

Change from baseline in EQ VAS will also be analyzed using the longitudinal ANCOVA model above to estimate within-treatment change from baseline and corresponding 95% CI at each time point.

PGIC

Percentage of participants with each response to the PGIC questionnaire will be summarized at each timepoint. Percentage of participants with improvements (either "very much improved" or "much improved" on the PGIC scale) will also be summarized at each time point.

Table 1 summarizes the analysis strategy for efficacy endpoints.

Table 1 Analysis Strategy for Efficacy Endpoints

Endpoint / Variable (Description / Timepoint)	Statistical Method	Analysis Population	Missing data approach
Secondary objective			
Change from baseline in LCQ total score	Longitudinal ANCOVA [†]	FAS	Model-based
% of participants who had an increase in the total score of ≥ 1.3 points from baseline	Descriptive statistics	FAS	Data as observed
Exploratory objective #1			
Change from baseline in mean weekly CSD score	Longitudinal ANCOVA [†]	FAS	Model-based
% of participants who had a decrease in the total score of ≥ 1.3 and ≥ 2.7 points from baseline	Descriptive statistics	FAS	Data as observed
Exploratory objective #2			
Change from baseline in the EQ5D-5L index utility score	Longitudinal ANCOVA [†]	FAS	Model-based
Change from baseline in EQ VAS	Longitudinal ANCOVA [†]	FAS	Model-based
% of participants with each response to the PGIC questionnaire	Descriptive statistics	FAS	Data as observed
% of participants with improvements in the PGIC questionnaire	Descriptive statistics	FAS	Data as observed
[†] Longitudinal analysis of covariance model with terms for treatment, visit and the interaction of treatment by visit, and baseline value as a covariate			
LCQ = Leicester Cough Questionnaire, CSD = Cough Severity Diary, EQ5D-5L = EuroQoL 5 Version Five Dimensions Questionnaire, PGIC = Patient Global Impression of Change, ANCOVA = analysis of covariance, FAS = Full Analysis Set.			

3.6.2 Statistical Methods for Safety Analyses

Safety and tolerability will be assessed by clinical review of all relevant parameters including AEs, study treatment discontinuations due to AE, laboratory tests, vital signs measurements.

All safety analyses will be based on the APaT population.

AEs and other safety events will be summarized using the number and percentage of the participants who experienced respective events. The AEs observed up to 14 days after the last dose will be included in the analysis.

Taste-related AEs (including dysgeusia, ageusia, and hypogeusia, as well as other related terms) and oral paraesthesia/hypoesthesia are considered as AEs of interest.

Continuous measures such as changes from baseline in laboratory, vital signs parameters will be summarized using descriptive statistics.

Summary statistics for baseline, on treatment, and change from baseline values will be provided in table format.

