4 STUDY DESIGN

4.1 Overall Design

This is a randomized, no treatment controlled, parallel-group, multi-site, double-blinded study of MK-7264 in Japanese adult participants with refractory or unexplained chronic cough.

Approximately 160 participants who meet entry criteria will enter the study. The study duration for each participant is as follows:

- Screening Period: a minimum of 7 days and up to 14 days. For those who need to washout therapy, the washout starts after obtaining the informed consent and the screening period starts from the completion of washout.
- Baseline/Randomization: Day 1
- Treatment period: 52 weeks
- Follow-up period: 14 days

Individual participation is expected to be approximately 56 weeks from Screening through the Follow-up period.

Specific procedures to be performed during the study, as well as their prescribed times and associated visit windows, are outlined in the SoA in Section 1.3. Details of each procedure are provided in Section 8.

At study entry, participants will be randomized in 1:1 ratio to 1 of 2 treatment groups: MK-7264 45 mg twice daily (BID) or MK-7264 15 mg BID. Participants should remain on their assigned treatment throughout the study period.

A safety follow-up telephone contact will be conducted at a minimum of 14 days (with an allowed variance of up to +7 days) after last dose of study intervention. Please refer to details in Section 8.10.6.

There will be one planned interim analysis when all the randomized participants have completed Week 24, or discontinued prior to Week 24. The initial database lock (to support the interim analysis) and all safety and efficacy analyses will be performed on the data up to Week 24. The sponsor will be unblinded at this point in order to analyze and report the data as the result will be used for the regulatory filing of MK-7264 in Japan. The study team responsible for the ongoing monitoring of the study will remain blinded to the treatment-level results of this interim analysis (safety and efficacy). The final database lock will be conducted when all participants have completed or discontinued prior to the completion of study.

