7 DISCONTINUATION OF STUDY INTERVENTION AND PARTICIPANT WITHDRAWAL

7.1 Discontinuation of Study Intervention

Discontinuation of study intervention does not represent withdrawal from the study.

As certain data on clinical events beyond study intervention discontinuation may be important to the study, they must be collected through the participant's last scheduled follow-

up, even if the participant has discontinued study intervention. Therefore, all participants who discontinue study intervention prior to completion of the protocol-specified treatment period will still continue to participate in the study as specified in Section 1.3 and Section 8.10.5.

Participants may discontinue study intervention at any time for any reason or be discontinued from the study intervention at the discretion of the investigator should any untoward effect occur. In addition, a participant may be discontinued from study intervention by the investigator or the Sponsor if study intervention is inappropriate, the study plan is violated, or for administrative and/or other safety reasons. Specific details regarding procedures to be performed at study intervention discontinuation are provided in Section 8.1.9.

A participant must be discontinued from study intervention but continue to be monitored in the study for any of the following reasons:

- The participant requests to discontinue study intervention.
- The participant's treatment assignment has been unblinded by the investigator, MSD subsidiary, or through the emergency unblinding call center.
- The participant has a medical condition or personal circumstance which, in the opinion of the investigator and/or Sponsor, placed the participant at unnecessary risk from continued administration of study intervention (including recommendation to discontinue participant from study intervention as part of monitoring for crystalluria/urolithiasis, see Section 8.3.7).
- The participant has a confirmed positive serum pregnancy test.
- In case of clinically significant and potentially drug related rash or signs and/or symptoms consistent with allergic drug reaction or anaphylaxis to study intervention.
- Chronic failure to comply with the dosing, evaluations, or other requirements of the study, despite documentation at the site of repeated efforts to reinforce compliance.

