8.10.5 Discontinued Participants Continuing to be Monitored in the Study

If a participant is discontinued from the study intervention early, the Discontinuation Visit assessments are to be performed as soon as possible.

It is intended that all participants should be followed through completion of the study, regardless of premature discontinuation of intervention unless the participant withdraws consent. Thus, participants who discontinue from study intervention prior to completion of the study should continue to be monitored to obtain relevant information through the end of the study. Study site visits/telephone calls should be made at timepoints that correspond to each remaining study visit. The follow-up information, limited to AEs, concomitant medication use, and patient report outcomes (site visits only) will be collected as outlined in the SoA.

Concomitant therapies specifically prohibited (see Section 6.5) while the participant was on study intervention are no longer prohibited after discontinuation of study intervention.

For these participants who have discontinued study intervention early, sites will be instructed to exert diligent efforts to continue to contact them. To enable sites to reach participants, the participants should provide primary and secondary contact information (eg, home telephone, work telephone, mobile telephone). Sites must document the outcome of the telephone contact(s), to demonstrate diligent efforts have been made. If a participant does not agree to be contacted for follow-up for each of the remaining visits (as described in Section 7.1), the participant should be encouraged to accept a telephone contact at least at Visit 8 date.

Additionally, the ICF will explain the importance of continued data collection from participants, including the use of continued contact by telephone.

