9.6.2 Statistical Methods for Safety Analyses

Safety and tolerability will be assessed by clinical review of all relevant parameters including AEs, study treatment discontinuations due to AE, laboratory tests, vital signs measurements.

All safety analyses will be based on APaT population.

AEs and other safety events will be summarized using the number and percentage of the participants who experienced respective events.

Taste-related AEs (including dysgeusia, ageusia, and hypogeusia, as well as other related terms) and oral paraesthesia/hypoesthesia are considered as AEs of interest.

Continuous measures such as changes from baseline in laboratory, vital signs parameters will be summarized using descriptive statistics.

Summary statistics for baseline, on treatment, and change from baseline values will be provided in table format.

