3.7 Interim Analyses

All efficacy analyses will be performed based on the data up to Week 24 when all the randomized participants have completed Week 24 or discontinued prior to Week 24. Safety analysis will include all available data up to the cutoff date for the interim database lock. Regardless of the result of the interim analysis (safety and efficacy), the study will continue as planned. Double blinding only to treatment assignment will be maintained at all investigational sites after all participants have completed Week 24. The results of interim analyses (safety and efficacy) will not be shared with the investigators prior to the completion of the study. The study will continue as double-blind only after Week 24 acknowledging that the sponsor will be unblinded at that point in order to analyze and report the data. The study team responsible for the ongoing monitoring of the study will remain blinded to the treatment-level results of this interim analysis (safety and efficacy).

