Appendix: Relative day ranges

Since it is not always possible for all study participants to come in for their clinic visits on the exact day specified in the protocol schedule, the following relative day ranges will be defined for each time point.

	Scheduled day	LCQ, CSD, vital signs	EQ5D-5L, PGIC, laboratory parameters	Body weight
Baseline	1	Day \leq 1	Day \leq 1	Day \leq 1
Week 4	28	2 \leq Day \leq 41	--	2 \leq Day \leq 55
Week 8	56	42 \leq Day \leq 69	--	--
Week 12	84	70 \leq Day \leq 125	2 \leq Day \leq 125	56 \leq Day \leq 125
Week 24	168	126 \leq Day \leq 216	126 \leq Day \leq 266	126 \leq Day \leq 266
Week 38	266	217 \leq Day \leq 315	--	--
Week 52	365	316 \leq Day	267 \leq Day	267 \leq Day

For the analysis of safety parameters, Day at post-baseline timepoints must be \leq 14 days following the last dose.
The analysis week for CSD will be defined based on the day of study visit by subjects. Seven (7) days to 1 day before the study visit will be used as the measurements for the analysis week to which the study visit day belongs.

If a subject has data on multiple days within a day range, the measurement closest to the scheduled day within the day range will be used in the analysis. If there are observations before and after the scheduled day that are equally apart from the scheduled day, then the observation after the scheduled day will be used for analysis. If two or more measurements are obtained on the same day, the average will be used as the observation for the day.

Baseline variable is defined as the last non-missing value prior to treatment. Typically this is the measurement taken at Visit 1 or Visit 2, depending on the endpoint.

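### The sSAP's AE analysis window closes 14 days after the last dose, and neither document says where later AEs, SAEs and deaths, which the protocol collects in early stoppers, are displayed

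*Combined protocol and SAP*

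**What the plan says.** **Collection.** Protocol Section 7.1 gives the reason for following participants off drug: "As certain data on clinical events beyond study intervention discontinuation may be important to the study, they must be collected". Section 8.10.5 lists what is gathered: "The follow-up information, limited to AEs, concomitant medication use, and patient report outcomes (site visits only) will be collected as outlined in the SoA". Section 8.4.1 defines an off-intervention reporting period that runs from the post-treatment safety call to the last off-intervention contact. Within that period, Table 3 still asks for all non-serious AEs, SAEs and cancers. Its footnote waives only ECIs, pregnancy or lactation exposure, and overdose.

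**Analysis.** Protocol Section 9.6.2 gives no time window: "AEs and other safety events will be summarized using the number and percentage of the participants who experienced respective events". sSAP Section 3.6.2 repeats that rule and adds the limit: "The AEs observed up to 14 days after the last dose will be included in the analysis". The sSAP appendix on relative day ranges sets a matching limit for other safety data: "For the analysis of safety parameters, Day at post-baseline timepoints must be" no later than 14 days after the last dose.

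**Interim.** sSAP Section 3.7, with the same content in 3.1, says: "Safety analysis will include all available data up to the cutoff date for the interim database lock". It does not mention the 14-day limit.

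**Efficacy, for contrast.** Under sSAP Section 3.6.1, unless specified otherwise, "analyses will include all follow-up efficacy data collected for those participants who discontinued treatment".

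**The concern.** The primary objective is safety and tolerability through 52 weeks, and the plan expects nearly half of the participants to stop drug before then. The protocol makes a deliberate effort to keep collecting AEs from them. For off-drug efficacy data the sSAP says explicitly that they are used. For off-drug safety data it states a window that leaves them out of the AE summaries, and it names no other place for them.

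A delayed serious event or death in someone who stopped, for example because of intolerance, would be in the database but in no summary that the plan describes. Whether and how to show it would then be decided after unblinding, when the events are known.

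Two smaller ambiguities make this worse. The sSAP speaks of events observed within the window and does not say whether that means onset or detection. The post-treatment safety call may fall anywhere from 14 to 21 days after the last dose (protocol Sections 4.1 and 8.10.6), so completers are affected too. An event that starts on post-dose day 10 and is found on day 18 is inside the window by onset and outside it by detection.

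**Working it through.** **1. The plan's own figures.** These come from sSAP Section 3.9 (protocol 9.9).
- Completers: 160 × (1 − 0.47) = 84.8; the plan states 84.
- Early stoppers: 160 − 84 = 76, and 76/160 = 47.5%.
- Chance of at least one AE at 2% incidence: 1 − 0.98^84 = 0.817 and 1 − 0.98^42 = 0.572, matching the stated 82% and 57%.

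The figures reproduce, and none depends on the AE window. The documents give no figure for follow-up after the window, so the rest is conditional.

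**2. Follow-up beyond last dose + 14 days, everyone followed to Day 378.** Day 378 (Week 54) is the last contact in the Schedule of Activities. For a stop on day t, the time outside the window is 378 − (t + 14) = 364 − t days.
- Uniform stopping over 52 weeks (mean stop Week 26): 76 × (54 − 28)/52.18 = 37.9 person-years.
- Constant hazard: h = −ln(84/160)/364 = 0.00177 per day. Mean time outside the window per randomized participant = 364 − (1 − 84/160)/h = 364 − 268.3 = 95.7 days. Total = 160 × 95.7/365.25 = 41.9 person-years.

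**3. Sensitivity to stop time and retention.** Person-years outside the window = 76 × retained share × (54 − (stop week + 2))/52.18. In brackets is the chance of at least one event, 1 − exp(−0.02 × person-years), at an assumed 2 events per 100 person-years.

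| Stop time | 100% retained | 50% retained | 25% retained |
|---|---|---|---|
| All at Week 4 | 69.9 (0.753) | 35.0 (0.503) | 17.5 (0.295) |
| All at Week 12 | 58.3 (0.688) | 29.1 (0.442) | 14.6 (0.253) |
| Uniform, mean Week 26 | 37.9 (0.531) | 18.9 (0.315) | 9.5 (0.172) |
| All at Week 40 | 17.5 (0.295) | 8.7 (0.160) | 4.4 (0.084) |

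The Week 54 endpoint for early stoppers is inferred from the Schedule of Activities. Section 8.10.5 says only that they are monitored to the end of the study. For those who refuse the remaining visits, it encourages at least one call at the Visit 8 date. Ending at Week 52 instead would take off about 76 × 2/52.18 = 2.9 person-years at full retention.

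**4. Does another passage cover the later events?**
- sSAP 3.7 sets a calendar cutoff. sSAP Section 2.0 describes the change as widening the interim safety scope to that date. It neither keeps nor lifts the 14-day limit, and it does not govern the final analysis.
- Protocol 9.6.2 has no window, but the sSAP supplies the analysis detail and states one. If the protocol text were to govern instead, the two documents would differ on which AEs count.
- The appendix rule concerns safety parameters. It has little effect off drug, because Section 8.10.5 limits that follow-up to AEs, concomitant medication and PROs. It does show that the 14-day limit in 3.6.2 is deliberate.

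**The case against.** A 14-day window is a sound choice for the main table. The protocol gives a half-life of about 7 to 10 hours (Section 4.3.3), so 14 days, or 336 hours, is some 34 to 48 half-lives. Taste effects are described as rapidly reversible (2.3), there is no placebo arm, and therapies prohibited on drug are allowed after stopping (8.10.5). Late events would be hard to attribute. All of this stands, and it is why the main table should not change.

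It can also be said that neither document itemises safety displays: no SAE table, death table or AE listing is named even for on-treatment events. That is fair as far as it goes. Here, however, the plan is not merely silent. It states an inclusion limit, which serves no purpose unless later events fall outside it.

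A reader might infer three stronger things that the documents do not support:
- *That late events go unreported.* Table 3 requires SAEs to reach the sponsor within 24 hours, including in participants off drug, and Section 8.4.4 covers onward reporting to authorities, ethics committees and investigators.
- *That no planned safety output could contain them.* Read literally, the interim sentence could include late events that occur before the cutoff, protocol 9.6.2 has no window, and sSAP 3.6.2 does not use a word such as only. Exclusion is the natural reading but is not spelled out.
- *That following early stoppers yields nothing, or that a lost SAE is close to certain.* Their PRO data are analysed under sSAP 3.6.1. A high probability of a lost SAE needs full retention and an SAE rate that appears in neither document.

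**Conclusion.** The point holds as a gap in tabulation. The protocol collects AEs, SAEs and cancers in early stoppers to their last off-intervention contact, the sSAP limits the AE analysis to 14 days after the last dose, and neither document describes a display for later events. The interim sentence is best read as a calendar cutoff. It leaves open whether the 14-day limit applies at the interim and does nothing for the final analysis.

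The central size is about 38 to 42 person-years outside the window, given 76 early stoppers, full follow-up to Day 378, and uniform or constant-hazard stopping. Over the stop times and retention levels examined, the range is about 4 to 70 person-years, with an 8% to 75% chance of at least one excluded event at 2 per 100 person-years. Stop timing, retention and the event rate are assumptions. No sample-size figure, estimate or decision rule depends on this, so it is an inexpensive improvement to the safety reporting and not a flaw in the design.

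**What to change.** In sSAP Section 3.6.2:

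1. Keep the 14-day on-treatment summary as the main AE table, and define its window by the date of AE onset.
2. Add one supplementary display, by arm and total, of deaths, SAEs and drug-related AEs with onset more than 14 days after the last dose through the last contact. Give with it the number of participants followed beyond that day and the number followed to Week 52, so that an absence of events can be read against the follow-up obtained.
3. State, in 3.6.2 or 3.7, whether the 14-day limit applies to the interim safety data.

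The cost is a few sentences and one table or listing from data already collected. The downside is that a few events unrelated to drug will be shown; a display separate from the on-treatment table contains that.
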